## **1.0 GOALS AND OBJECTIVES**

To study the efficacy of the combination of reduced dose craniospinal radiation (reduced from standard of care dosing at 36 Gy to 24 Gy) with concurrent carboplatin and vincristine administration for metastatic classical histology medulloblastomas and high-risk supratentorial PNETs and metastatic PNETs.

## **2.0 OVERVIEW AND STUDY DESIGN**

This study is to look at the efficacy of reducing the dose of craniospinal radiation to limit adverse effects, while adding concurrent carboplatin administration during radiation with weekly vincristine for metastatic medulloblastomas and high-risk supratentorial PNETs and metastatic PNETs. Pilot data from Children's Oncology Group (COG) study 99701 show excellent results with daily carboplatin infusion during radiation for high risk central nervous system tumors (Jakacki et al, 2006). This study had an 89% 3 year event free survival for classical histology metastatic medulloblastoma. Anaplastic medulloblastomas did poorly and will be excluded from the current study.

Although the COG 99701 study had excellent event free survival, 36 Gy radiation dose to the craniospinal axis was used. This dosage is known to be associated with extremely poor quality of life as an adult (Ribi et al, 2005, Packer et al, 1994). The improvement of survival of COG 99701 over all prior studies appears to be due to the addition of carboplatin during radiation. The current study proposes to see if the addition of carboplatin during radiation allows for lowering the craniospinal radiation dose to 23.4 Gy, a dose which is known to be associated with a satisfactory quality of life for adult survivors (Ribi et al, 2005, Packer et al, 1994).

In order to assess efficacy we would accept equivalency in terms of 90% event free survival from progression at 3 years. We will re-assess the therapy after every 10 patients completes the study. One

failure within every ten patients would close the study. Following concurrent carboplatin, vincristine, and craniospinal radiation at 24 Gy, patients will receive the current standard adjuvant chemotherapy.

### **3.0 BACKGROUND AND RATIONALE**

PNET is a class of brain tumors that consists of medulloblastomas (in the cerebellum) and supratentorial PNETs. These are two subgroups of the same tumor type that have the same risk profile. They tend to metastasize through the cerebral spinal fluid pathways. PNETs are classified by the World Health Organization as grade IV tumors (highly malignant) (Kleihues & Cavenee, 2000). PNETs occur most commonly in children aged 4 weeks to 10 years, with peak age of diagnosis at age five. Up to one third of patients have metastatic disease at diagnosis (Kleihues & Cavenee, 2000). Disseminated disease has been found to be an adverse prognostic factor (Packer et al, 1994; Boyett et al, 1995). Other poor prognostic factors include primary tumors that are not cerebellar or pineal; age less than 3 years; and significant post-operative residual tumor (Cohen et al, 1995; Jenkin et al, 1990).

Adding chemotherapy to radiation is proposed to enhance the response on tumor burden (Steel, 1979). This increased response may occur because of increased cell death, decrease in radiation-induced damage repair, and prevention of tumor cell rebound growth in response to radiation therapy (Wilkins et al, 1993). Cells may also be induced out of the resting phase and become more chemo and radio-sensitive. It is also postulated to eliminate systemic micrometastases concurrently to the primary tumor.

It is known that platinum can potentiate the efficacy of radiation (Douple & Richmond, 1978). Platinum radiosensitizes hypoxic cells and possibly keep tumor cells in the radiosensitive phase of the cell cycle (Skov & MacPhail, 1991; Douple et al, 1985). Inhibition of “sublethal damage repair” and “potentially lethal damage recovery” is caused by the potentiation of radiation biochemically (Fu &

Phillips, 1991). This has been demonstrated by cisplatin in a brain tumor cell line (Wilkins et al, 1993). In addition, chromosomal aberrations may be increased (Schwachoffer et al, 1991).

Frequent low-dose carboplatin administration has been shown to be surprisingly effective in several pediatric brain tumors. This sensitivity to low-dose carboplatin is currently unexplainable by standard modeling (Mastangelo et al, 1995; Gaynon et al, 1990). Seven of 15 patients with recurrent PNET treated with weekly doses of carboplatin showed response to treatment (Allen et al, 1987). The majority of patients received 175 mg/m^2/week. Only low tissue levels of carboplatin are necessary to be radiosensitizing because the unbound drug has a half-life of 6 hours (Albers & Mason-Liddil, 1989). Therefore, the recent national cooperative group study chose to use 35 mg/m^2/day to establish sufficient radiosensitizing levels (Jakacki et al, 2006).

Daily administration of platinum during fractionated radiotherapy has shown positive results in solid tumors (Bartelink et al, 1986; Schaake-Konig et al, 1992; Jakacki et al, 2006). Concurrent chemotherapy and radiation with lower continuous dosing appears to have more effect on tumor cells than normal tissue with reduction of acute and late toxicities (Schaake-Konig et al, 1992; Steel, 1988; Jeremic et al, 1995; Jeremic et al, 1996). A trial of concurrent cisplatin and radiotherapy in patients with non-small cell lung cancer improved survival and local disease control compared to radiation alone (Schaake-Konig, 1992). Weekly cisplatin with radiation showed no significant difference. Esophagitis was not increased, but nausea and vomiting occurred in most patients. Head and neck cancer patients on a Phase I/II study of concurrent carboplatin and radiation had significantly improved survival rates than historical data with sequential chemoradiotherapy (Volling et al, 1992).

Glioblastoma multiforme patients were treated with Carboplatin (33mg/m^2) daily for five days during the first and fourth week of radiation therapy. Toxicity included Grade III and IV neutropenia in 25% of the patients and thrombocytopenia in 10% of patients. Neurotoxicity from radiation necrosis was not higher than in patients with radiation alone (Levin et al, 1995). Ausili-Cefari et al, gave

continuous infusion Carboplatin at a dose of 30 mg/m^2/day for either 14 or 21 days during radiation therapy to head and neck cancer patients. Only the patients who had carboplatin for 21 days had leukopenia and thrombocytopenia. There were no serious infections. Six of twelve patients developed mucositis, none requiring interruption of treatment (Ausili-Cefaro et al, 1995). A Phase I study of bi-weekly Carboplatin during radiation therapy for children with brain stem gliomas showed a mean tolerated dose of 280 mg/m^2/week for seven weeks (Allen et al, 1995).

Craniospinal irradiation has improved the survival rates for medulloblastoma, but it has also been implicated in poor quality of life related to impaired cognitive functioning that worsens over time (Packer, 1989). Radcliffe et al showed that whole-brain radiotherapy decreases IQ. Age is inversely correlated with loss of IQ. Children younger than 7 at diagnosis showed a significant loss of IQ points (Radcliffe et al, 1992).

Ribi, et al, (Ribi et al, 2005) followed 51 children who were consecutively diagnosed with medulloblastoma. Only two of the patients did not receive radiation because they were less than 3 years old. The other children received between 23.4-36.0 Gy craniospinal irradiation and with a boost of 48.0-55.0 Gy irradiation to the tumor bed. Significant deficits in neurocognitive functioning were seen in all of the patients. They had concurrent endocrine deficits (61%), neurological complications (72%), and significant school problems (72%)

Reduced dose craniospinal radiation has been shown to decrease the cognitive deficits. Mulhern et al demonstrated, in 22 children with medulloblastoma, that less severe neuropsychologic injury occurred when treated with only 23.4 Gy instead of 36 Gy craniospinal radiation. Once again, age was correlated with toxicity, with older children experiencing fewer cognitive deficits than younger children (Mulhern et al, 1998).

Goldwein, et al, treated 10 children diagnosed with medulloblastoma between 18 and 60 months of age with reduced craniospinal radiation . The patients received reduced dose craniospinal

radiation, a radiation boost to the tumor bed and standard maintenance chemotherapy. Survival at over 6 years was 70%, which is the accepted national survival rate for medulloblastoma with 36 Gy craniospinal radiation. The survivors had minimal neurocognitive damage, but did have decreased growth rates (Goldwein et al, 1996).

We therefore propose extending the benefits of reduced dose craniospinal radiation to metastatic medulloblastoma patients and high-risk, non-metastatic supratentorial PNET patients, and metastatic PNET patients by adding the concurrent carboplatin to the reduced dose radiation. Data regarding neuropsychologic outcome in children treated for non-metastatic medulloblastoma, with 36 Gy craniospinal radiation, and the same maintenance chemotherapy (Packer et al, 2006) is available, and will serve as a control group to assess the benefit of a reduced radiation dose.

## **4.0 METHODS**

### **4.1 Eligibility Criteria**

#### **Inclusion Criteria**

- Age greater than 3 years and less than 25 years.
- Patients with one of the following diagnoses by histological diagnoses and by head and spine MRI:
  - Classic histology metastatic medulloblastoma
  - Desmoplastic histology metastatic medulloblastoma
  - High-risk supratentorial, non-metastatic, PNET
  - Metastatic PNET
- Newly diagnosed patients who have not received prior therapy, with the exception of one short course of emergent chemotherapy in newly presenting patients with neurological compromise per provider decision
- Only patients who are expected to survive at least 6 weeks will be eligible for this study.

## **Exclusion Criteria**

- Anaplastic histology will be excluded
- Patients who are pregnant may not be treated on this study

## **4.2 Subject Enrollment**

Approximately 10 subjects will be enrolled locally at Children's Hospital Colorado. Eligible subjects will be offered participation in the study by their primary physician through the Neuro-Oncology Program at Children's Hospital Colorado. The subjects may be inpatients or outpatients.

## **4.3 Informed Consent Procedure**

The investigator (or designee) will obtain written informed consent/assent from each subject or their authorized representative who participates in the study, before the initiation of any study procedures. All physicians, nurses, and study coordinators who are involved with the study and may perform any or all parts of the consent process have been educated in research principles and certified by taking the applicable COMIRB education course(s). The consent/assent will be explained in an environment that is private, quiet, and conducive to effective communication. Explanation will be given at the level of comprehension of the consentee. A dialogue between the subject and/or parent and the investigator will confirm the understanding and agreement to participate.

## **Non-English Speaking Subjects**

This study will follow the COMIRB guidelines regarding Non-English speaking subjects, per the following from the COMIRB Instructions for Clinical Investigators:

45 CFR 46.117 (b)(2) permits oral presentation of informed consent in conjunction with a short form stating that the elements of informed consent have been presented orally, for studies that will include non-English speaking subjects but not purposely recruit them. A study is permitted to utilize the short

form up to three times in the same language. If a 4th subject is to be enrolled then a translation of the entire consent form should be provided.

After the English version is approved, a translated consent form should be obtained by the investigator and submitted to COMIRB. The credentials of the translator must be provided to COMIRB. The translator must have expertise (native language or evidence of fluency) in the language including medical and legal terminology, in order to translate consent forms. When the translated consent form is used with a subject, the person obtaining consent and the subject or their representative will sign the non-English consent form.

A translator fluent in the subject's language and English must read the consent summary to the subject or their representative. A written summary of what is presented orally is also required. A witness to the oral presentation is required, and the translator can also serve in this role. The subject or their representative and the witness (translator) must sign the Short Form. The person obtaining consent as authorized under the protocol and the witness (translator) must sign the Consent Summary. The subject must be given copies of the Short Form document and the Consent Summary. The investigator must have a plan for how to answer the subject's questions and assess comprehension in the subjects' native language. The subject or his/her representative walks away with: (1) the short form written consent in the subject's language; (2) the long standard consent in English; (3) a copy of the summary of the oral presentation.

Forms required for oral presentation of consent:

- Short Form. This must state that the **elements** of consent have been presented orally to the subject and it must be in the language the subject is fluent in. A template of the Short Form is available in a variety of languages on the COMIRB web site under Forms. The subject or their representative and the witness, who in most cases is the translator, must sign this form. Consent Summary. The COMIRB approved English language consent form can serve as

the consent summary. The person obtaining consent and the witness (translator) should sign this.

Health outcomes on all subjects will be studied, but only an English-speaking subset will be measured for neuropsychologic outcomes due to the limitations of the testing measures used in this study in order to compare to the control group.

#### **4.4 Confidentiality**

The clinical and laboratory data for each patient are part of their medical records at Children's Hospital Colorado. Laboratory data are computerized at CHCO and accessible to authorized staff that have a laboratory password. Patient data will also be entered into Children's Hospital Colorado Neuro-Oncology Program database. This information will be used by the principal investigator for data collection and analysis and will only be accessible to qualified staff working on this research project. The database is a secure, password-protected database. Completed data forms for each patient on study at Children's Hospital Colorado will be kept in locked cabinets, accessible only to study team members. The clinical research associates will monitor the level of authorization/consent signed by the patient to assure that authorization has been obtained for release of all data that are released.

#### **4.5 HIPAA Authorization Procedure**

Written authorization will be obtained at the time the consent is obtained, as this study will collect protected health information from the subjects. The principal investigator(s) or qualified designee will explain the HIPAA regulations in the combined consent/HIPAA authorization form. The clinical research associates will assure that the consent/HIPAA authorization form has been properly signed and dated prior to study entry, and that the subject/parent receives a copy of the signed and dated form. The program database will contain the date the consent/HIPAA authorization form was signed. Information will be released only to those specified in the consent/HIPAA authorization form.

## **5.0 TREATMENT PROGRAM**

### **5.1 Chemoradiotherapy**

Within 28 days of diagnosis, patients will start radiation therapy, at a dose of 24 Gy. The craniospinal axis will be treated first. Daily carboplatin will be given at 35 mg/m^2 IV over 15-20 minutes Monday through Friday, approximately 1-4 hours prior to radiation for 6 weeks (total of 30 doses). Weekly Vincristine will be given at 1.5 mg/m^2 (standard therapy) for 6 weeks.

Following radiation, patients will receive the current national standard of maintenance chemotherapy with a cisplatin backbone. Maintenance chemotherapy will always reflect the national cooperative group's evidence-based standard of care. Subjects will be followed during maintenance, but no research testing will be conducted during this standard of care chemotherapy. The first dose of carboplatin should be administered on the first day of radiation therapy, unless the patient needs emergent treatment, in which case carboplatin may be administered prior to the first day of radiation therapy. Carboplatin will be administered in 25 ml NS IV over 15 minutes approximately 1-4 hours prior to radiation therapy. This should be sufficient time for patients who may require sedation or who travel to another facility.

If a radiation treatment is not given, carboplatin should be held as well. If a dose of carboplatin is given and radiation therapy is NOT administered due to sedation or technical issues, the carboplatin dose should not be made up at the end of radiation (i.e. no more than 30 doses of carboplatin should be given). Since there are 31 fractions of radiation, the last radiation treatment will not be preceded by a dose of carboplatin.

Pregnancy tests will be done per standard of care protocol at screening and prior to any treatments. Subjects should not be pregnant prior to starting the study, or become pregnant, nurse a child, or father a baby while on this study because the study treatment may harm an unborn baby, nursing child, or pregnant female. Subjects must use effective birth control while on this study.

Subjects will be counseled by the medical staff regarding this issue as necessary. Any pregnancy that inadvertently occurs in a study subject or a partner of a subject must be reported to COMIRB as an unanticipated problem with the required documents and the study will be re-reviewed at that time.

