## 12.3 Treatment Volume Anatomical Description

### 12.31 Treatment Volumes

Definitions:

- Gross Target Volumes (GTV): The Gross Target Volume (GTV) is based upon the T1 weighted MRI with and without Gadolinium contrast. Identification of the GTV shall be based upon pre-operative extent and anatomic shifts or changes after surgery. The GTV should include any residual enhancing tumor mass and the wall of the resection cavity.
- Clinical Target Volume (CTV): The Clinical Target Volume (CTV) is defined as the GTV plus a 1.5-cm margin
- Planning Target Volumes (PTV): The Planning Target Volume (PTV) margin should be an additional 0.3 to 0.5 cm around the CTV, depending on the setup error of the treatment modality used. In treatment planning, shielding of critical structures should be attempted. At least 95% of the prescribed study dose (55.8 Gy) must encompass at least 95% of the PTV as shown by DVH. No part of the PTV should receive less than 50 Gy.
- Treated Volume (TV): The volume enclosed by an isodose surface that is selected and specified by the radiation oncologist to which the prescribed dose is delivered.

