### 12.53 Total Treatment Dose

#### 12.531 Craniospinal Axis

All patients will receive 23.4 Gy to the craniospinal axis.

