#### 12.532 Primary Site Boost

All patients with primary tumor in the posterior fossa will receive a boost of 32.4 Gy to the posterior fossa. All patients with a supratentorial primary tumor will receive a boost 32.4 Gy to the volume described in section 12.3. As noted there, the total dose to the optic chiasm and both optic nerves should be limited to 50.4 Gy. In addition, if the boost volume occupies more than 2/3 of the supratentorial compartment, the boost dose should be limited to 27 Gy.

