#### 12.533 Metastatic Site Boost

Patients with M1 disease will receive no additional boost. Patients with M2 disease (intracranial subarachnoid disease) will receive boosts of 32.4 Gy to focal areas of supratentorial or posterior fossa metastatic disease. If the volume of a boost to the supratentorial compartment exceeds 2/3 of the

supratentorial compartment volume, the boost will be limited to 27 Gy. The boost dose to the optic chiasm and both optic nerves must be limited to 27 Gy. 3D treatment planning may be used for boosting M2 disease. If 3D planning is used, definitions boost volumes for M2 disease will be the same as specified for boosts to the primary tumor. Patients with M3 disease (spinal deposits of disease) are subdivided into those with diffuse disease and those with focal disease. Diffuse spinal disease is defined as radiographically visible multiple sites of disease in each of at least 3 out of 4 spinal regions (i.e., cervical, thoracic, lumbar or sacral).

If there is diffuse involvement of the spine, the entire spine will be treated to 23.4 Gy. An MRI scan of the spine should be performed when the spine has received 23.4 Gy, and areas of visible disease remaining at that point should be boosted to 45 Gy when above the termination of the spinal cord and 50.4 Gy when below the termination of the cord. If there are focal areas of spinal deposits which do not meet the definition of diffuse involvement defined above, the entire spine will be treated to 23.4 Gy. The focal areas of tumor seen on the initial spinal MRI will be boosted to 45 Gy. Focal deposits below the termination of the cord as defined by the initial MRI will be boosted to 50.4 Gy. The margin for boosting metastatic deposits will be at least 7 mm, and preferably 10 mm.

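### The craniospinal dose under test is 24 Gy in some sections and 23.4 Gy in others, and photons are mandatory in 12.21 while protons are allowed in 12.41

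*Protocol*

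**What the plan says.** **Dose.** All references are to the Protocol.

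- Section 1.0 (objective): "reduced from standard of care dosing at 36 Gy to 24 Gy".
- Section 2.0, second paragraph: the aim is "lowering the craniospinal radiation dose to 23.4 Gy".
- Section 2.0, last paragraph: "craniospinal radiation at 24 Gy".
- Section 5.1 (treatment program): "patients will start radiation therapy, at a dose of 24 Gy". The next sentence names the craniospinal axis as the first target. The same section counts 31 radiation fractions and caps carboplatin at 30 doses.
- Section 12.531: "All patients will receive 23.4 Gy to the craniospinal axis".
- Section 12.533, for spinal deposits, whether diffuse or focal: "the entire spine will be treated to 23.4 Gy".

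The related figures are the primary boost in 12.532 ("All patients with primary tumor in the posterior fossa will receive a boost of 32.4 Gy to the posterior fossa", with the same size for supratentorial primaries), the daily dose of 180 cGy in 12.541, and the total in 12.31, repeated in 12.34: "At least 95% of the prescribed study dose (55.8 Gy) must encompass at least 95% of the PTV".

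**Modality.** Section 12.21 prescribes photons in mandatory terms. Section 12.22 permits electrons for the spine. Section 12.41 lists proton therapy among the acceptable volume-based systems, subject to criteria. Section 12.4 applies 3D planning to whole brain, spinal axis and boosts; 12.32 makes it optional for the boost; 12.34 makes it compulsory for the posterior fossa boost.

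**The concern.** The study tests whether the craniospinal dose can be lowered from 36 Gy when carboplatin is given during radiation. That dose appears with two values, in the objective, design, treatment and radiotherapy sections, and section 2.0 contains both. Section 5.1 tells the team what to give, and its figure differs from the one in 12.531.

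Under 13.33, a favourable result in 10 patients would go to the national group as a candidate for a randomized Phase III study. Whoever takes it up needs to know which regimen was tested.

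On modality, a patient treated with protons would comply with 12.41 and breach 12.21. The retrospective radiotherapy quality review in 12.7 would then have no single rule to apply to that patient.

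**Working it through.** **Inputs.** Craniospinal dose: 23.4 Gy (2.0 second paragraph, 12.531, 12.533) or 24 Gy (1.0, 2.0 last paragraph, 5.1). Primary boost: 32.4 Gy (12.532). Daily dose: 1.8 Gy (12.541). Stated results: 31 fractions (5.1) and 55.8 Gy (12.31, 12.34).

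**Formulas.** Total dose = craniospinal dose + boost. Fractions = total dose / 1.8.

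**Step 1: reproduce the protocol's own figures, then repeat with 24 Gy.**

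| | 23.4 Gy | 24 Gy |
|---|---|---|
| Craniospinal fractions | 23.4/1.8 = 13.00 | 24/1.8 = 13.33 |
| Boost fractions | 32.4/1.8 = 18 | 32.4/1.8 = 18 |
| Total fractions | 31.00 | 31.33 |
| Total dose | 23.4 + 32.4 = 55.8 Gy | 24 + 32.4 = 56.4 Gy |
| Matches 31 fractions and 55.8 Gy? | yes | no |

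**Step 2: can 24 Gy be given in whole fractions of 180 cGy?** No. 13 × 1.8 = 23.4 Gy and 14 × 1.8 = 25.2 Gy. Exactly 24 Gy would need 2400/13 = 184.6 cGy or 2400/14 = 171.4 cGy per day.

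**Step 3: other figures that depend on the craniospinal dose.**

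- Optic structures: 12.533 limits the boost to 27 Gy, and 12.35 and 12.532 limit the total to 50.4 Gy. 23.4 + 27 = 50.4 Gy equals the limit; 24 + 27 = 51.0 Gy exceeds it.
- Spinal deposits boosted to 45 or 50.4 Gy (12.533): from 23.4 Gy, (45 − 23.4)/1.8 = 12 and (50.4 − 23.4)/1.8 = 15 fractions. From 24 Gy, (45 − 24)/1.8 = 11.67 and (50.4 − 24)/1.8 = 14.67.

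**Step 4: size of the gap.** 24 − 23.4 = 0.6 Gy; 0.6/23.4 = 2.6%. The reduction from 36 Gy is 36 − 24 = 12.0 Gy by one set of passages and 36 − 23.4 = 12.6 Gy by the other.

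This arithmetic shows which statements agree with each other. It does not settle which dose is clinically intended.

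**Step 5: modality, by comparing the text.** The mandatory wording in 12.21 exempts no field. The one departure nearby, in 12.22, concerns electrons for the spine, not protons. The permission in 12.41 sits under 12.4, which covers whole brain, spine and boosts. The planning scan in 12.42 need reach only C3, which suggests that a narrower scope may have been meant. Even if 12.41 applied only to boosts, it would cover the posterior fossa boost, where 12.34 requires 3D planning. The two rules therefore overlap in at least one field on any reading.

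**The case against.** **Dose.** The section that prescribes dose is not itself ambiguous. 12.531 and 12.533 agree, and the daily dose, the boost, the total, the optic limits and the 31 fractions all fit 23.4 Gy. A team following 12.541 could not deliver 24 Gy in whole fractions. Section 2.0 uses both figures for what is plainly one regimen, which looks like rounding in summary text. The sentence in 5.1 does not itself name the craniospinal axis.

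Much of this stands, and it limits the practical risk. It does not remove the mismatch. No passage calls 24 Gy a rounded figure or gives section 12 precedence. The sentence after the one in 5.1, together with 1.0 and 2.0, ties the figure to the craniospinal axis. The rationale in 2.0 about quality of life is attached to 23.4 Gy specifically.

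**Modality.** Section 12.22 already departs from a pure photon rule, and elsewhere section 12 sets a conventional default beside a provision for 3D planning (12.523, 12.65). On that view 12.41 is a conditional permission alongside a general equipment statement. A photon plan can satisfy 12.21, 12.34 and 12.41 together, so no patient is forced into a breach.

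That last point is correct: the conflict arises only if a site chooses protons. But 12.41 gives sites that choice and 12.21 denies it, and the electron allowance does not extend to protons.

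**Consequence.** It is also fair that no analysis result turns on either point.

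**Conclusion.** The protocol is wrong as written on both points. The craniospinal dose has two values 0.6 Gy apart (2.6% of 23.4 Gy), and the 24 Gy figure does not fit the 31 fractions stated in the same section 5.1 once the boost and daily dose from section 12 are applied. The photon requirement and the proton permission contradict each other.

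The dose comparison assumes the full 32.4 Gy boost and 180 cGy per day throughout, as 12.532 and 12.541 state. The number of patients who might receive protons is not given; it could be anything from 0 to all of the roughly 10 planned.

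The weight is moderate. This is an inconsistency in the definition of the tested regimen, so it should be corrected. No effect of the 0.6 Gy on event-free survival or intellectual outcome is claimed, no passage makes inclusion in the analysis depend on modality, and the sample size and decision rule do not change.

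**What to change.** - Reconcile 1.0, both paragraphs of 2.0, 5.1, 12.531 and 12.533 so that each gives the same craniospinal dose, or state once that one figure is rounded and which section governs. Check the result against the fraction count in 5.1, the total in 12.31 and 12.34, the daily dose in 12.541 and the optic limits in 12.35, 12.532 and 12.533.
- Reconcile 12.21 with 12.41 so that the permitted modalities, and the fields to which each applies, are stated in one place. Align 12.4, 12.32 and 12.42 with that scope.

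Which dose and which modalities apply is for the sponsor to settle; none is proposed here. The cost is a wording amendment, with no change to sample size, decision rule, visits or data collection.
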